8. CRITERIA FOR OUTCOME ASSESSMENT/THERAPEUTIC RESPONSE

8.1 **Outcome Assessment**

All baseline evaluations will be performed as closely as possible to the beginning of treatment (within 7 days). For subsequent evaluations, the method of assessment and techniques will be the same as those used at baseline.

- Tumor markers

PSA measurements will be used to assess the primary endpoint.

8.1.1 *Primary endpoint*

The primary endpoint is defined as a PSA₅₀ response, defined as a decline in PSA to 50% of baseline level, confirmed with a second measurement at least 4 weeks apart.

8.1.2 Secondary endpoints

8.1.2.1. Safety: this endpoint is defined as incidence of grade 3-5 toxicities based upon CTC v4.0 standard grading scales.

8.1.2.2. PSA Progression-Free Survival (PFS): PSA PFS is a time to event endpoint defined as from initiation of olaparib therapy until an increase in PSA of 25% over a nadir value, confirmed with a second measurement at least 4 weeks apart. The date of PSA progression will be the first value recorded (not the confirmatory value).

8.1.2.3. Time to PSA doubling from baseline: this endpoint is a time-to-event defined as time from initiation of olaparib therapy until the PSA has increased to 200% of baseline value, confirmed with another measurement at least 4 weeks later. The date of PSA doubling will be the first value recorded (not the confirmatory value).

8.1.2.4. Undetectable PSA: This endpoint represents a durable complete response to therapy. It is defined as a PSA of <0.1 confirmed with a repeat measurement at least 12 weeks later.

8.2 Therapeutic Response

Response and progression will be evaluated in this study using guidelines for prostate cancer endpoints developed by the Prostate Cancer Clinical Trials Working Group (PCWG3). Because the population under study in this protocol has only a biochemical manifestation of disease, response is primarily evaluated based upon changes in PSA.

9. DATA REPORTING AND REGULATORY REQUIREMENTS

Multicenter Guidelines

The Protocol Chair

The Protocol Chair, [name] [name], is responsible for performing the following tasks:

- Coordinating, developing, submitting, and obtaining approval for the protocol as well as its subsequent amendments
- Assuring that all participating institutions are using the correct version of the protocol
- Taking responsibility for the overall conduct of the study at all participating institutions and for monitoring the progress of the study
- Reviewing and ensuring reporting of Serious Adverse Events (SAEs)
- Reviewing data from all sites

Lead Center

The Lead Center (Johns Hopkins) is responsible for performing the following tasks:

- Ensuring that IRB approval has been obtained at each participating site prior to the first patient registration at that site, and maintaining copies of IRB approvals from each site.
- Managing central patient registration
- Collecting and compiling data from each site
- Establishing procedures for documentation, reporting and submitting of AE's and SAE's to the Protocol Chair and all other applicable parties.
- Facilitating audits by securing selected source documents and research records from participating sites for audit, or by auditing at participating sites.

Participating PCCTC Sites

Participating sites are responsible for performing the following tasks:

- Following the protocol as written, and the guidelines of Good Clinical Practice (GCP).
- Submitting data to the Lead Center
- Registering all patients with the Lead Center by submitting patient registration form, and signed informed consent promptly
- Providing sufficient experienced clinical and administrative staff and adequate facilities and equipment to conduct a collaborative trial according to the protocol
- Maintaining regulatory binders on site and providing copies of all required documents to the Lead Center
- Collecting and submitting data according to the schedule specified by the protocol

9.1 Data Entry

Data collected during this study will be entered into a secure database. Staff at the PCCTC coordinating center at MSKCC will be responsible for the initial study configuration and setup in the consortium database and for any future changes.

9.1.1 Case report forms

Case report forms will be generated by the coordinating center at MSKCC for the collection of all study data. Investigators will be responsible for ensuring that the CRFs are kept up-to-date.

9.1.2 Source documents

Study personnel will record clinical data in each patient's source documents (ie, the patient's medical record). Source documentation will be made available to support

the patient research record. Study monitors will review entries on the CRFs at regular intervals, comparing the content with source documents.

9.1.3 Record retention

The investigator will maintain adequate and accurate records to enable the conduct of the study to be fully documented and the study data to be subsequently verified. After study closure, the investigator will maintain all source documents, study-related documents, and the CRFs. Because the length of time required for retaining records depends upon a number of regulatory and legal factors, documents should be stored until the investigator is notified that the documents may be destroyed. In this study, records are to be retained and securely stored for a minimum of 5 years after the completion of all study activities.

9.2 Data Management

9.2.1 Lead research program coordinators

A Lead research program coordinator at the coordinating center will be assigned to the study. A Lead Research Program Coordinator will manage the study activities at each of the participating sites. The responsibilities of the Lead Research Program Coordinator include project compliance, data collection, data entry, data reporting, regulatory monitoring, problem resolution and prioritization, and coordination of the activities of the protocol team.

9.3 Study Monitoring and Quality Assurance

Regularly scheduled registration reports will be generated to monitor patient accruals and the completeness of registration data. Routine data quality reports will be generated to assess missing data and inconsistencies. Accrual rates and the extent and accuracy of evaluations and follow-up will be monitored periodically throughout the study period, and potential problems will be brought to the attention of the principal investigator for discussion and action.

Random-sample data quality and protocol compliance audits will be conducted by the study team at least once a year, more frequently if indicated. Audits by the coordinating center may entail (1) shipping source documents and research records for selected patients from participating sites to the coordinating center for audit, or (2) on-site auditing of selected patient records at participating sites.

All clinical work conducted under this protocol is subject to Good Clinical Practice (GCP) guidelines. This includes inspection of study-related records by the lead site, sponsor, its designee, or health authority representatives at any time.

9.4 Clinical Trial Agreement

This trial is being conducted under one or more clinical trial agreements that contain, among other terms, the publication policy, indemnity agreements, and financial arrangements for the study.

9.5 SKCCC Data and Safety Monitoring Plan

The SKCCC Compliance Monitoring Program will provide external monitoring for JHU

affiliated sites in accordance with SKCCC DSMP (Version 6.0, 02/21/2019). The SMC Subcommittee will determine the level of patient safety risk and level/frequency of monitoring.

10. STATISTICAL CONSIDERATIONS

This study will enroll up to 50 subjects. The study design will employ a stepwise adaptive statistical plan, derived in part from Biankin *et al.* [27]. The design is adapted from a multi-stage design, with interim stopping rules to determine futility or need for enrichment of the study population.

The study will initiate with a two-stage design in an unselected population. The assumptions for the trial of the unselected population are: null hypothesis of 0.1 PSA response rate and alternative hypothesis of 0.3 for the unselected population. The first stage is 20 subjects. If ≤ 2 subjects respond in the first stage, then unselected population study is halted for futility and an assessment of DNA mutations present in the initial cohort will be undertaken. If less than 3 subjects with a known/suspected deleterious mutation in the following genes (ATM, BARD1, BRCA1, BRCA2, BRIP1, CDK12, CHEK1, CHEK2, FANCL, PALB2, PPP2R2A, RAD51B, RAD51C, RAD51D or other DNA repair genes) have been accrued in the first stage, then the trial will proceed with enrichment. If 3 or more subjects with known/suspected deleterious mutation in the genes of interest have been accrued, then the trial will proceed with enrichment, as long as the response rate in that subset of subjects is $\geq 20\%$. In the case that 3 or more subjects have been accrued, yet the response rate in that subset is $< 20\%$, then the trial is halted for futility.

However, if ≥ 3 subjects among the first 20 respond, then additional 10 unselected subjects are accrued. If ≥ 6 subjects respond out of 30 in the unselected population after the second stage, then the null hypothesis is rejected in the unselected population and broad efficacy will be concluded. The trial proceeds to complete accrual of 50 subjects in order to better estimate PSA response rate and strengthen data for correlative studies. If < 6 respond, then the null hypothesis is not rejected. Again, if less than 3 subjects with a known/suspected deleterious mutation in the following genes (ATM, BARD1, BRCA1, BRCA2, BRIP1, CDK12, CHEK1, CHEK2, FANCL, PALB2, PPP2R2A, RAD51B, RAD51C, RAD51D or other DNA repair genes) have been accrued in the first and second stage combined, then the trial will proceed with enrichment. If 3 or more subjects with those mutations have been accrued, then enrichment will again proceed as long as the response rate in that subset of subjects is $\geq 20\%$.

An enriched population will be required to have a known/suspected deleterious mutation in the genes listed above. The data for the enriched population will be analyzed separately from the data in the first (and second, if applicable) stage(s). The assumptions for the enriched population: null hypothesis of 0.3 PSA response rate, and alternative hypothesis of 0.6 for the biomarker selected population. The sample size for the selected population is 20 subjects. If ≥ 10 respond, the null is rejected for the biomarker selected population and efficacy will be concluded for the biomarker subgroup.

This design will have power for detecting an effect in the unselected population of 0.90-0.91 and a power for detecting an effect in the selected population (if there is no effect in the

unselected) of 0.79-0.80, with an overall type I error 0.1-0.11, assuming the biomarker prevalence 10-15%, based upon 10,000 simulations of possible outcomes.

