10.2 Operating Characteristics of Clinical Trial Design

The operating characteristics of the multi-stage adaptive design were illustrated in a 10,000-iteration simulation. The simulations employed the assumptions outlined above (unselected population study: alpha 0.10, power 0.90, $H_0 = 0.1$, $H_1 = 0.3$; selected population study: alpha 0.10, power 0.80, $H_0 = 0.3$, $H_1 = 0.6$) in a 50 subject study.

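### The 20-carrier enriched cohort has no futility look; adding one after 10 carriers is a cheap improvement, not the correction of an error

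*Combined protocol and SAP*

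**What the plan says.** Section 10 (and the synopsis, Study Design) gives the unselected part two stages: 20 men, then 10 more if at least 3 of the 20 respond, with success at 6 or more of 30.

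If the unselected part fails, a carrier gate decides whether enrichment opens. The first branch begins "If less than 3 subjects with a known/suspected deleterious mutation in the following genes" and, when so few carriers "have been accrued in the first stage, then the trial will proceed with enrichment". With 3 or more carriers, "then the trial will proceed with enrichment, as long as the response rate in that subset of subjects is" at least 20%. After stage 2 the same gate is applied to both stages combined.

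The enriched cohort is analysed separately. Its hypotheses are "null hypothesis of 0.3 PSA response rate, and alternative hypothesis of 0.6 for the biomarker selected population". Its size is fixed ("The sample size for the selected population is 20 subjects") and it has one decision rule: "If ≥ 10 respond, the null is rejected for the biomarker selected population". Section 10.2 gives the targets as "selected population study: alpha 0.10, power 0.80". The operating characteristics are stated as "assuming the biomarker prevalence 10-15%, based upon 10,000 simulations of possible outcomes".

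No interim look inside the enriched cohort is described. The only other stopping provisions are the MDS/AML rule (section 10.1.2.1, Safety) and general termination (section 11.5).

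**The concern.** The plan describes itself as multi-stage with interim rules for futility, yet the last cohort, where the biomarker hypothesis is tested, has none. If carriers do not respond well enough, the only earlier protection is the gate. It cannot act when fewer than 3 carriers were accrued, and with 3 to 5 carriers a single responder passes it, since 1/5 = 20%.

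At stake is exposure. These men have non-metastatic disease, for which the synopsis names surveillance as a standard option, and the drug has a risk of MDS/AML that the synopsis calls rare but life threatening. A cohort with 2 or fewer responders in its first 10 would still enrol 10 more carriers with little chance of a positive result.

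**Working it through.** **Inputs.** From section 10: enriched n = 20, success at ≥10, p0 = 0.3, p1 = 0.6; unselected rules ≤2 of 20 and ≥6 of 30; gate at 3 carriers and 20%; prevalence 10% and 15%. From sections 10.2.1 and 10.2.3: the simulated proportions. The non-carrier rate is (all-comer rate − prevalence × carrier rate)/(1 − prevalence). All results below are exact binomial.

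**1. The plan's figures reproduce.** For the enriched rule alone, P(X ≥ 10 | 20, 0.3) = 0.0480 and P(X ≥ 10 | 20, 0.6) = 0.8725. Enumerating the whole design with all-comers at 0.10 and carriers at 0.60, enrichment opens with probability 0.915 (10% prevalence) or 0.907 (15%). Biomarker power is 0.915 × 0.8725 = 0.80 and 0.907 × 0.8725 = 0.79, as stated.

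**2. How much the gate stops (all-comers 0.10).** The plan's figure is stage 1 plus stage 2 futility without enrichment.

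| Carrier rate | Prevalence | Gate stops, plan | Gate stops, exact | Enrichment futility, plan | Exact |
|---|---|---|---|---|---|
| 0.30 | 10% | 0.09 + 0.03 = 0.12 | 0.11 | 0.78 | 0.783 |
| 0.30 | 15% | 0.15 + 0.03 = 0.18 | 0.18 | 0.72 | 0.713 |
| 0.20 | 10% | 0.12 + 0.05 = 0.17 | 0.17 | 0.76 | 0.754 |
| 0.20 | 15% | 0.23 + 0.07 = 0.30 | 0.30 | 0.62 | 0.629 |

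The 0.30 rows are in section 10.2.1; the 0.20 rows are scenarios 2 and 31. Because the cohort has no earlier rule, every enrichment-futility trial has enrolled all 20 carriers.

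**3. Why the gate is limited.** P(fewer than 3 carriers) among the first 20 is 0.68 at 10% prevalence and 0.40 at 15%. Among 30, which applies if stage 2 was run, it is 0.41 and 0.15.

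**4. The proposed look.** Stop if X1 ≤ 2 of the first 10; otherwise continue to 20 and require ≥10.
- Early stop = P(X1 ≤ 2 | 10, p).
- Rejection = Σ over x = 3..10 of P(X1 = x) × P(X2 ≥ 10 − x | 10, p).
- Expected size = 10 + 10 × (1 − early stop).

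| True rate | Early stop | Rejection, one stage | Rejection, with look | Expected size |
|---|---|---|---|---|
| 0.20 | 0.678 | 0.0026 | 0.0026 | 13.2 |
| 0.30 | 0.383 | 0.0480 | 0.0476 | 16.2 |
| 0.40 | 0.167 | 0.2447 | 0.2431 | 18.3 |
| 0.50 | 0.055 | 0.5881 | 0.5856 | 19.5 |
| 0.60 | 0.012 | 0.8725 | 0.8706 | 19.9 |

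The largest loss is 0.25 percentage points, near a rate of 0.50. Whole-design biomarker power goes from 0.799 to 0.797 (10% prevalence) and from 0.792 to 0.790 (15%).

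**5. Chance of success after 2 of 10.** At least 8 of the next 10 are needed: probability 0.0016 at 0.30, 0.00008 at 0.20 and 0.167 at 0.60.

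**6. Sensitivity to late responses.** Suppose, as an assumption, that only a fraction of the eventual responses in the first 10 are confirmed at the look and the rest count as failures there. Power at 0.60 falls to 0.835 if 80% are visible and 0.784 if 70% are visible.

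**The case against.** The strongest reply is that this is a design preference. The single-stage rule beats both of its stated targets, no section promises a look inside this cohort, and the cohort is itself the last step of a multi-stage design with a gate in front of it. That stands, and it sets the status of the point: an efficiency gain, not a defect.

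A second reply is that the look is hard to run. PSA50 response has no time window: it counts whenever it occurs on therapy, with confirmation at least 4 weeks later, so a man still on olaparib without a response has no settled status. This stands in part. The plan already uses the same endpoint for its stage 1 decision, so the difficulty is not new, but step 6 shows that the small power cost depends on settled statuses.

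Third, stopping at 10 leaves little information: at 2 of 10 the exact 95% interval is 2.5% to 55.6%, and the primary objective is estimation. Exposure is also partly limited already by the individual PSA-doubling criterion (section 6.4) and the MDS/AML rule. Both are true and should be weighed.

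A reader might also infer more than the documents support:
- That the gate hardly ever stops a failing biomarker. In the scenarios above it stops 11% to 30% of trials. At the 19-23% tissue prevalence in section 1.3.1 the exact figures are about 22-25% at a carrier rate of 0.30 and 38-43% at 0.20, though about half or more of trials still run to 20.
- That 2 of 10 makes success impossible. It does not (step 5).
- That each carrier costs a fixed number of men sequenced, or that carriers will arrive too slowly for an accrual pause to matter. Section 5.1 lets men with documented prior somatic or germline results enrol directly, and the plan gives no carrier accrual rate.

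**Conclusion.** The point holds as a cheap improvement. The enriched cohort runs to 20 with no futility look, and under the plan's own unfavourable scenarios that is the most common outcome: 72-78% of trials at a carrier rate of 0.30 and 62-76% at 0.20.

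The 38% and 68% early-stop figures are conditional on the enriched cohort opening and on true carrier rates of 0.30 and 0.20. As a share of all trials they are 0.822 × 0.383 = 31% and 0.756 × 0.678 = 51% at 10% prevalence, and 0.749 × 0.383 = 29% and 0.630 × 0.678 = 43% at 15%. The look can only remove rejections, so type I error cannot rise and the final threshold needs no change.

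The result rests on independent binomial responses, the plan's prevalence range and an all-comer rate of 0.10, and statuses settled at the look. The saving in men enrolled also assumes that accrual pauses or is slow enough for the look to come before many more carriers have entered.

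**What to change.** In section 10 and the synopsis, write the enriched cohort as two stages. After the first 10 enriched carriers have a known status, stop the cohort for futility if 2 or fewer have a confirmed PSA50 response; otherwise continue to 20 and keep success at 10 or more.

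Define a man's status as known for the look once he has a confirmed response, has stopped olaparib without one, or has completed a response window that the sponsor fixes in advance. State whether accrual pauses while the first 10 are awaited. Then rerun the simulation and update the tables in section 10.2, including the expected enriched cohort size.

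The cost is at most about 0.25 percentage points of power if statuses are settled (more if late responses are counted as failures), and a wide interval and less correlative data if the cohort stops at 10.

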10.1 Study Endpoints

10.1.1 Analysis of the primary endpoint

The primary endpoint of this study is PSA₅₀ response, defined as a decrease in the PSA to 50% less than the baseline PSA upon enrollment in the trial. The decrease must be confirmed by a second measurement at least 4 weeks apart. For purposes of meeting the primary endpoint, patients will be considered to have done so if they have a PSA₅₀ response only while on therapy with olaparib. The confirmatory value may be drawn off therapy for olaparib. PSA values will be measured each cycle during the trial. All patients who are administered at least one dose of olaparib will be considered evaluable for the primary endpoint. If patients do not have follow-up PSAs after initiation olaparib therapy due to stopping therapy for toxicity or withdrawing consent, for example, then they will be considered non-responders. If the biomarker-enriched stage is necessary, that cohort will be evaluated separately from the initial stage(s) of the trial.

We will estimate the PSA₅₀ response rate, along with the exact 95% confidence interval, for the population of patients. If a biomarker-selected population is accrued, it will be analyzed separately from the previously accrued unselected population.

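### The 95% interval for the PSA50 rate in the unselected cohort has no named method that allows for the response-dependent stops; read in the usual way it is not exact, with a small effect

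*Combined protocol and SAP*

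**What the plan says.** The primary objective (Section 2.1) is to estimate the PSA50 response rate. Section 10.1.1 gives the analysis in one sentence, which says that the rate is to be reported "along with the exact 95% confidence interval, for the population of patients". The synopsis (Statistical Methods, part c) also speaks of estimating the rate and gives no interval.

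Section 10 makes the size of the unselected sample depend on the data:

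- Stage 1: "The first stage is 20 subjects". The futility rule at that point reads: "If ≤ 2 subjects respond in the first stage, then unselected population study is halted for futility".
- Stage 2: "if ≥ 3 subjects among the first 20 respond, then additional 10 unselected subjects are accrued". The test then uses both stages together: "If ≥ 6 subjects respond out of 30 in the unselected population after the second stage, then the null hypothesis is rejected". With fewer than 6 responders, unselected accrual ends at 30.
- Extension after rejection: "The trial proceeds to complete accrual of 50 subjects in order to better estimate PSA response rate".

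The hypotheses are a "null hypothesis of 0.1 PSA response rate and alternative hypothesis of 0.3 for the unselected population". The tables in Section 10.2 report rejection and futility probabilities. They do not report the bias of the estimate or the coverage of the interval. Any enriched cohort has a fixed size of 20 and is analysed separately.

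**The concern.** A fixed-sample exact binomial interval guarantees at least 95% coverage when N is set in advance. Here N is itself an outcome: low response counts end the sample early, and only better counts run to 50. The guarantee then no longer applies automatically, and x/N is pulled downward because poor early results are never diluted by further patients. Since estimation is the stated primary objective and the extension to 50 exists for estimation, the reported rate and its interval should have the properties their names imply. At stake is how a low-to-middling result is read, for example whether the interval excludes the alternative of 0.30.

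**Working it through.** **Inputs (all from Section 10).** Stop at 20 if x ≤ 2; stop at 30 if x ≤ 5; otherwise continue to 50. H0 = 0.10, H1 = 0.30. The possible end points are 0–2 of 20, 3–5 of 30, and 6–50 of 50.

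**Step 1: reproduce the plan's own figures.** P(reject) = Σ over a = 3 to 20 of P(Bin(20,p) = a) × P(Bin(10,p) ≥ 6 − a).

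- p = 0.10: 0.0691 (Section 10.2.1 gives 0.07).
- p = 0.30: 0.9126 (Section 10 gives 0.90–0.91).
- p = 0.15, 0.20 and 0.25: 0.277, 0.554 and 0.781, in line with the all-comer power column of the scenario table that closes Section 10.2.

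**Step 2: bias of x/N.** E[x/N] is the sum over the end sizes of P(N) × mean of x/N given N.

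- p = 0.20: 0.206 × 0.0804 + 0.240 × 0.1496 + 0.554 × 0.2309 = 0.0166 + 0.0359 + 0.1279 = 0.1804, a bias of −0.020.
- p = 0.30: 0.0355 × 0.0881 + 0.0519 × 0.1561 + 0.9126 × 0.3082 = 0.0031 + 0.0081 + 0.2813 = 0.2925, a bias of −0.0075.
- By the same sum: −0.012 at 0.10, −0.019 at 0.15 and −0.014 at 0.25. The largest value is −0.0205, at about 0.177.

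**Step 3: coverage of the fixed-sample Clopper-Pearson interval.** Sum the probabilities of all end points whose interval contains p.

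| True rate | Coverage |
|---|---|
| 0.10 | 0.983 |
| 0.20 | 0.974 |
| 0.25 | 0.961 |
| 0.30 | 0.974 |
| 0.317 | 0.934 (minimum) |
| 0.35 | 0.943 |
| 0.40 | 0.966 |

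On a grid of 0.001 from 0.001 to 0.999, coverage is below 0.95 at 43 of 999 points, all between 0.317 and 0.374.

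The minimum can be taken apart. The upper limit for 2/20 is 0.31698, so just above it every stop at 20 misses, with probability 0.0250 by construction. Two end points at 30 also miss from below:

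- 3/30: C(20,3) = 1140 paths, 1140 × 0.317³ × 0.683²⁷ = 0.0012.
- 4/30: C(20,3) × 10 + C(20,4) = 16,245 paths, 16,245 × 0.317⁴ × 0.683²⁶ = 0.0081.

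The end points 6–9 of 50 add 0.0080. The total upper-side miss is 0.0250 + 0.0012 + 0.0081 + 0.0080 = 0.0423, against a nominal 0.025. The lower-side miss is 0.0240. Coverage is 1 − 0.0423 − 0.0240 = 0.9337.

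With N fixed, the minimum Clopper-Pearson coverage is 0.958, 0.954 and 0.953 for N = 20, 30 and 50. The shortfall therefore comes from the stopping rule.

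**Step 4: an interval built from the design.** Order the end points as 0–2 of 20, then 3–5 of 30, then 6–50 of 50, and invert the two 2.5% tails. The UMVUE, which is E[x₁/20 | N, x] with x₁ the stage-1 count, rises along this list, so stage-wise and UMVUE ordering give the same interval. Its minimum coverage is 0.951.

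| Result | x/N (fixed-sample interval) | UMVUE (design-based interval) |
|---|---|---|
| 3/30 | 10.0% (2.1–26.5) | 15.0% (3.2–31.9) |
| 5/30 | 16.7% (5.6–34.7) | 18.5% (5.9–35.6) |
| 8/50 | 16.0% (7.2–29.1) | 21.9% (8.7–35.6) |
| 10/50 | 20.0% (10.0–33.7) | 23.4% (10.7–36.4) |
| 15/50 | 30.0% (17.9–44.6) | 30.4% (17.9–44.7) |

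At 3/30 and 8/50 the fixed-sample interval excludes 0.30 and the design-based one does not. From about 15/50 upward the two agree closely.

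**Step 5: precision of the two estimates.** The root-mean-square error of x/N against that of the UMVUE is 0.053 against 0.064 at p = 0.10 and 0.064 against 0.072 at 0.15. The two are about equal at 0.20, and the UMVUE is better above that.

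**The case against.** The plan does not name Clopper-Pearson, does not name x/N, and nowhere says that the stops will be ignored. A design-based interval is also exact, so a reader who infers that the plan has chosen a wrong method goes further than the text. That objection stands: what the documents show is an unnamed method, and the coverage figures rest on the usual reading of the term.

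A reader might also infer that the interval generally covers at about 93%. It does not. The value 0.934 is a dip just above the upper limit for 2/20; by 0.32 coverage is back to 0.947, and at both design hypotheses the interval is conservative. Bias and under-coverage do not coincide either: bias peaks near 0.18, where coverage exceeds 0.97, and it is under 0.6 points where coverage is short.

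A third tempting reading is that the trial's decisions are distorted. Section 10 decides on pre-set counts at 20 and 30 and sets no threshold at 50. No decision uses the interval.

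Finally, the shortfall needs the extension to 50. If only the 20/30 test design is analysed, minimum coverage is 0.951 and the largest bias is 1.0 point. This is correct, but Section 10 specifies the extension for the purpose of estimation, so it belongs in the calculation.

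**Conclusion.** The point holds in a limited form. In its usual reading, the exact 95% interval of Section 10.1.1 does not have the guaranteed coverage under the 20/30/50 rule: the minimum is 0.934, and the shortfall is confined to parts of 0.317–0.374. The proportion x/N underestimates by at most about 2 points. The go/no-go rules, type I error, power and the enriched cohort are untouched.

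The figures do not support replacing x/N with the UMVUE as the primary estimate. That would trade a small bias for a larger root-mean-square error at true rates below about 0.20, and would report 6/50 as 20.9% instead of 12.0%.

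Assumptions: Clopper-Pearson limits are applied to the final N; each stage fills exactly to 20, 30 or 50; and the safety stop for MDS/AML is left out. If the sponsor already intends a stage-adjusted interval, one sentence saying so closes the point.

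**What to change.** In Section 10.1.1:

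- State that the 95% interval for the unselected cohort is an exact interval from the 20/30/50 sample space, and name the ordering (stage-wise or by the UMVUE).
- Keep x/N as the reported rate and show the UMVUE beside it as a supportive, bias-adjusted estimate.
- Keep the fixed-sample exact interval for the enriched cohort, where N is fixed at 20.

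The method should be fixed before results are known, because the candidate intervals can disagree about 0.30. The cost is SAP wording and a few lines of code, with no change to sample size, decision rules or conduct. The drawbacks are a less familiar interval that is not centred on x/N at low counts, and a second estimate that differs visibly from x/N there and needs a line of explanation.
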